 - H1a. The percentage of MI interviews in the first 40 consecutive, study-eligible inpatients identified by the research team will be higher in the "DO ONE" than "SEE ONE" group;
 - H1b. The percentage of MI interviews in the first 40 consecutive, study-eligible inpatients identified by the research team will be higher in the "ORDER ONE" than "SEE ONE" group.
2. To assess the integrity of MI when Healthcare providers use it on the medical units.
 - H2a. DO ONE will result in more proficiently conducted MI sessions than SEE ONE;
 - H2b. ORDER ONE will result in more proficiently conducted MI sessions than SEE ONE.
3. To assess the cost-effectiveness of the three strategies.
 - H3a. SEE ONE will be the most cost-effective implementation strategy when the threshold value to decision makers of inpatients receiving an additional MI session to a criterion level of adequate performance is relatively low;
 - H3b. DO ONE and ORDER ONE will be more cost-effective than SEE ONE when the threshold value is relatively high.

The primary outcome for MI *uptake* will be the percentage of MI sessions conducted for study-eligible inpatients as verified by audio recordings. For MI *proficiency*, primary outcomes will be 1) independently rated MI adherence and competence ratings of the sessions, and 2) the percentage of sessions achieving a criterion level of adequate MI performance used in MI effectiveness¹⁸⁻²⁰ and clinician training trials.^{21,22} In addition, we will calculate the relative costs and cost-effectiveness of the three MI implementation strategies. Secondary outcomes across the three conditions will be 1) independently rated strength and frequency of patient statements that favor change in the sessions (called change talk) as a proxy for patient outcomes,^{23,24} and 2) themes related to implementation facilitators and barriers identified through qualitative assessment.

2. **Background:** Describe the background information that led to the plan for this project. Provide references to support the expectation of obtaining useful scientific data.

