Procedures for highly efficient, real-time managing, monitoring, and analysis of data have been developed and refined by our research group. We are using OnCore, Yale's new Clinical Trials Management System (CTMS), to track procedures and data entry for patient characteristics and outcomes. Participants enter data directly into the computer via CASI. All computers are encrypted and password protected. Identifying data are not kept on the computer. For office PCs where data that were collected on paper is entered, we use a double entry method (staff data) and regular data checks to assess the integrity of the data base and missing data. After data entry and cleaning, de-identified data are moved to SAS databases for analysis.

2. Data analysis for quantitative primary and secondary outcomes

Outlined below is the general strategy for data analyses which will address each of our specific aims: (1) assess the uptake of MI by Healthcare providers on the medical units; (2) assess the integrity of MI when Healthcare providers use it on the medical units; (3) assess the cost-effectiveness of the three strategies; (4) determine how long the initial training effects endure across the study period.

- *Data reduction:* Primary outcome variables have been defined *a priori* to reduce the risk of Type I error. Preparatory analyses will include evaluation of baseline equivalence of groups on demographic and comparability of rates of data availability across conditions. If imbalances exist we will enter the unbalanced variables as covariates in the models below. Descriptive statistics for all outcome variables will be calculated prior to statistical analysis. Continuous outcome

variables will be evaluated for normality and transformations will be applied as necessary. Two-sided tests and overall alpha level of 0.05 for all primary hypotheses will be used.

- *Strategies for management of differential attrition:* We do not expect differential attrition across conditions in that the rate of Healthcare provider job turnover is very low and their activities in the study overlap considerably with their normal duties. However, in the event of Healthcare provider discontinuation in the trial, we will recruit new Healthcare provider hires to maintain a balanced design.

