- *Evaluation of effects at implementation strategies:* The principal strategy for assessing the effectiveness of the study implementation conditions on outcome will be mixed effects general linear models for continuously measured primary (e.g., MI integrity) and secondary (e.g., strength and frequency of patient change talk) outcomes variables, and generalized linear mixed models for binary outcomes (e.g. meets criterion MI performance threshold). In both types of models we will have training condition as the main predictor variable and will include random effects for Healthcare providers to account for clustering of observations within Healthcare providers. Our main hypotheses involve group comparisons with the SEE IT group as the reference condition. We will consider significant comparisons of the DO IT and ORDER IT conditions to the SEE IT condition as supportive of our hypotheses. Comparisons of DO IT with ORDER IT will be conducted for exploratory purposes only.

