- *Adequacy of sample size for primary hypotheses:* Effect sizes for power estimation for the continuous outcomes were based on studies by Miller et al.²³ (d=0.4 to 0.8) and [name] et al.²¹ (d=0.4 to 1.2). A review article by Apodaca and Longabaugh¹⁴⁸ also suggests that at least medium effect sizes are expected for the between-group comparisons. [name] et al.²¹ observed large effect sizes for the binary outcome comparison (meets criterion MI performance threshold, 53% vs. 18%); however, we conservatively assume a medium effect size for this comparison as well. Intra-class correlations accounting for expected within clinician variance were estimated based on Imel et al¹⁴⁹ and are expected to be small (in the 0.05 to 0.10 range). Feasibility constraints (i.e., 10 Healthcare providers per condition) limited the number of clusters (Healthcare providers) that we could consider. Finally, because we do not expect all Healthcare providers to identify substance using patients and use MI with them (i.e., our 1st hypothesis about MI uptake), we will require a larger sample size of study-enrolled patients to reach our targeted number of audio recorded MI sessions for hypothesis testing purposes. We estimate 80% of patients across conditions will receive MI. Based on these estimates and constraints, alpha level of 0.05 and power of 80%, 30 Healthcare providers and 40 patients per Healthcare provider will be sufficient for testing the primary hypotheses of the study. Table 2 shows the actual total sample size for the cluster-randomized design for continuous and binary outcomes, adjusted for a conservative estimate of MI uptake.

Table 2: Sample size estimates for the primary aims of the study based on alpha=0.05 for the pairwise comparisons of each condition to the control condition and 80% power.

Effect size	Total sample size for an ordinary RCT (3 arms)	ICC	Number of Healthcare provider	Average number of patients per Healthcare provider	Total sample size for a cluster RCT unadjusted for estimated MI uptake	Total sample size for a cluster RCT adjusted for estimated MI uptake
d=0.4	300	0.07	31	31	930	1116
40% vs 18%	195	0.1	30	17	510	765

3. Incremental cost-effectiveness analyses

The relative cost-effectiveness of the three MI implementation strategies will be assessed using both incremental cost-effectiveness ratios (ICERs) and cost-effectiveness acceptability curves (CEACs).

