SECTION VII: RECRUITMENT/CONSENT AND ASSENT PROCEDURES

1. **Targeted Enrollment: Give the number of subjects:**
a. targeted for enrollment at Yale for this protocol __see below__
b. If this is a multi-site study, give the total number of subjects targeted across all sites __n/a__

Participants will be Physician Assistants (PAs) who work at the Yale New Haven Hospital (YNHH) Internal Medicine Hospitalist service and 1200-1600 inpatients who are being cared for by a PA from the Hospitalist Service. All PAs on the Internal Medicine Hospitalist service are eligible to participate. We will obtain written informed consent from all the PAs who express interest in participation and MI training. The PAs will be randomized to one of three conditions that are outlined below. The inpatients who may be eligible subjects will be followed for inpatient care by one of the Internal Medicine hospitalist service PAs. While they will not be randomized, they will follow the randomization condition of their PA. Additionally, we have expanded our target for enrollment to other Healthcare providers (i.e. nursing staff, physician, etc.) who work at Yale New Haven Hospital (YNHH) within general medical inpatient units. Between the PAs and other healthcare providers we intend to enroll 30-40 participants.

2. **Indicate recruitment methods below.** Attach copies of any recruitment materials that will be used.

- | | | |
|--|---|-------------------------------------|
|  Flyers |  Internet/Web Postings |  Radio |
|  Posters |  Mass E-mail Solicitation |  Telephone |
|  Letter |  Departmental/Center Website |  Television |
|  Medical Record Review |  Departmental/Center Research Boards |  Newspaper |
|  Departmental/Center Newsletters |  Web-Based Clinical Trial Registries | |
|  YCCI Recruitment database |  Clinicaltrials.gov Registry (do not send materials to HIC) | |
|  Other (describe): please see below | | |

3. **Recruitment Procedures:**
a. Describe how potential subjects will be identified.
b. Describe how potential subjects are contacted.

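### The plan promises an overall two-sided alpha of 0.05 for its primary hypotheses, but the trial is sized at 0.05 for each comparison with SEE ONE and no multiplicity rule is given.

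*Combined protocol and SAP*

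**What the plan says.** Section V.12, under Data reduction, sets the error rate: "Two-sided tests and overall alpha level of 0.05 for all primary hypotheses will be used". The same bullet says the primary outcomes were fixed in advance "to reduce the risk of Type I error".

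The bullet on evaluating the implementation strategies describes the tests: "Our main hypotheses involve group comparisons with the SEE IT group as the reference condition". DO ONE and ORDER ONE are each compared with SEE ONE, a significant result counts as support, and DO ONE against ORDER ONE is exploratory. No alpha level appears there.

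The title of Table 2 gives the sizing basis as "alpha=0.05 for the pairwise comparisons of each condition to the control condition and 80% power". The accompanying text concludes that "30 Healthcare providers and 40 patients per Healthcare provider will be sufficient for testing the primary hypotheses of the study".

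There is more than one primary outcome. Section V.1 has uptake (H1a, H1b) and proficiency (H2a, H2b). For proficiency it says "primary outcomes will be 1) independently rated MI adherence and competence ratings of the sessions", and adds the percentage of sessions reaching the performance criterion. The description of the ITRS splits the ratings into adherence and competence on each of two factors. The plan does not say which of these share the 0.05.

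**The concern.** An overall 0.05 and a separate 0.05 for each of two comparisons are different error rates, and the plan states both without a procedure linking them. As written, the promised property is not delivered even for one outcome.

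The consequence is practical. Suppose one comparison gives p between 0.025 and 0.05 and the other is clearly null. An analyst testing each comparison at 0.05 calls this a positive finding; one applying Holm or Bonferroni does not. Both could cite the same section, so the choice could be made after the results are known. If the overall level is enforced, the stated 80% power also needs to be recalculated.

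**Working it through.** **Inputs.** From Section V.12 and Table 2: two-sided 0.05, 80% power, three equal arms, 10 providers per arm, d=0.4 with ICC 0.07, 40% vs 18% with ICC 0.1, ICC range 0.05 to 0.10, and 80% uptake. Sessions per provider: 40 × 0.80 = 32.

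**1. Which alpha produced Table 2?** The table's totals before clustering are 300 and 195. Use n per arm = 2(z₁₋α/₂ + z₀.₈)² / effect², with the arcsine effect h = 2·asin√0.40 − 2·asin√0.18 = 0.493 for the binary row.

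- At 0.05, (1.960 + 0.842)² = 7.849. For d=0.4: 2 × 7.849/0.16 = 98.1 per arm, total 294. For the binary row: 2 × 7.849/0.493² = 64.6 per arm, total 194.
- At 0.025, (2.241 + 0.842)² = 9.505. The totals are 356 and 235.

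Rounding up per arm, with the t-test formula for d=0.4 and the arcsine formula for the binary row, gives exactly 100 × 3 = 300 and 65 × 3 = 195 at 0.05. At 0.025 the same formulas give 363 and 237. Table 2 therefore contains no adjustment.

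**2. Family-wise error at 0.05 per comparison.** With equal arms and a shared control, the two test statistics have correlation 0.5. Integrating the bivariate normal:

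- P(either |z| > 1.96) = 0.0907.
- P(either z > 1.96), the hypothesised direction only, = 0.0454.
- Two independent outcomes: 1 − (1 − 0.0907)² = 0.173. With an assumed correlation of 0.8 between outcomes it is about 0.14. The documents give no correlation.

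**3. Power for one named comparison.** Variance of the difference = 2[ICC/k + (1 − ICC)/(k·m)], with k providers per arm and m sessions each.

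- d=0.4: 2[0.07/10 + 0.93/320] = 0.01981, SE 0.1408, standardised effect 0.4/0.1408 = 2.84.
- 40% vs 18%: 2[0.1/10 + 0.9/320] = 0.02563, SE 0.1601, standardised effect 0.493/0.1601 = 3.08.

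Two-sided critical values (normal / t on 27 df, from 30 providers less 3 arms): unadjusted 1.960/2.052; Dunnett 2.212/2.333; Bonferroni 2.241/2.373. Holm was simulated with 2,000,000 trials.

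| Rule (normal / 27 df) | d=0.4, ICC 0.07, m=32 | 40% vs 18%, ICC 0.1, m=32 |
|---|---|---|
| Unadjusted 0.05 | 81% / 78% | 87% / 84% |
| Holm, both arms effective | 78% / 74% | 85% / 81% |
| Holm, one arm effective | 73% / 68% | 80% / 76% |
| Dunnett | 74% / 69% | 81% / 77% |
| Bonferroni 0.025 | 73% / 68% | 80% / 76% |

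At Table 2's own 17 sessions per provider, the binary row goes from 81%/78% unadjusted to 73%/69% with Dunnett.

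**4. Sensitivity of the d=0.4 row at 0.025 (m=32).**

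- ICC 0.05: 82% (normal). ICC 0.10: 60%, but only 70% even unadjusted. Power reaches 80% at an ICC near 0.055.
- 12 providers per arm (36 in all), ICC 0.07: 81% (normal) or 77% (33 df). Section VII.1 allows for this: "Between the PAs and other healthcare providers we intend to enroll 30-40 participants".
- d=0.5, taking this as a medium effect (an assumption), 10 per arm: 96%/94% at ICC 0.05, 91%/87% at 0.07 and 81%/77% at 0.10 (normal / 27 df).

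Table 2 has no uptake effect size, so the effect on H1a and H1b cannot be calculated.

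**The case against.** The strongest reply is that *overall* means one common significance level applied to every primary test. That fits Table 2 and the sample-size text, and on that reading only a word is wrong. It is a possible reading, but the plan does not say so, and the word sits in a bullet about limiting Type I error. An edit is needed either way.

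It can also be argued that separately stated hypotheses about two different strategies need no joint control. That is a defensible policy, but it is not the one the plan states.

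All four hypotheses are directional, and the chance of falsely supporting either one for a single outcome is about 4.5%. This is correct and puts the 9.1% in proportion. But the plan specifies two-sided tests, and the figure covers one outcome only.

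The loss of power is conditional. It largely disappears at d=0.5, at an ICC near 0.05, or with 36 providers, and the binary row holds up at 32 sessions. Part of the shortfall is not due to multiplicity: on 27 df the unadjusted d=0.4 figure is already 78%. These limits stand. Still, d=0.4, ICC 0.07 and 10 providers per arm are the plan's own design values, and at those values the stated 80% is not kept under an overall 0.05.

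Finally, the plan does fix the reference arm, the sidedness and the exploratory status of DO ONE against ORDER ONE. These steps narrow the family of tests but do not control error across those that remain.

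**Conclusion.** The concern holds and should be fixed. The plan claims an overall two-sided 0.05, sizes the trial at 0.05 per comparison, and gives no rule to reconcile them. For one outcome with two comparisons the resulting two-sided error is about 9.1%. The 17% figure for the four hypotheses assumes independent aims treated as one family, and whether control must span aims is the sponsor's decision.

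Enforcing 0.05 over the two comparisons lowers d=0.4 power at the plan's design values by about 3 to 10 percentage points, depending on the rule and on whether both arms work. These figures assume equal arms, equal sessions per provider and 80% uptake. The problem is one of specification and does not undermine the design itself.

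**What to change.** Reconcile the Data reduction bullet with Table 2 in one of two ways.

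**A. Keep the overall 0.05.** Name Holm or Dunnett for the two comparisons with SEE ONE within each primary outcome. State which primary outcomes share the 0.05. Restate the Table 2 power under that rule for the number of providers actually planned.

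**B. Give up family-wise control.** State that each comparison with SEE ONE is tested two-sided at 0.05 without adjustment, and remove *overall*. Table 2's alpha then stands.

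Both are changes of wording, plus a restated power line under A. Neither needs new patients or data. The price of A, at d=0.4, ICC 0.07 and 10 providers per arm, is lower stated power: about 3 to 5 points with Holm if both arms work, about 8 to 9 with Dunnett, and about 8 to 10 with Bonferroni or with Holm if only one arm works. It is more if outcomes are adjusted as well. The price of B is the claim of overall error control.

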Primary outcomes will be 1) the percentage of MI sessions, as verified by audio recordings, conducted among each Healthcare provider 40 consecutively enrolled study patients, 2) independently rated MI adherence and competence ratings of the sessions, and 3) the percentage of sessions conducted that meet a criterion level of adequate MI performance used in MI effectiveness¹⁸⁻²⁰ and clinician training trials.^{21,22} In addition, we will calculate the relative costs and cost effectiveness of the three conditions. Secondary outcomes will be 1) independently rated strength and frequency of patient statements that favor change in the sessions (called change talk) as a proxy for patient outcomes,^{23,24} and 2) themes related to implementation facilitators and barriers identified through qualitative interviews. The YNHH hospitalist and the psychiatric CL services will work closely with research staff to implement all aspects of this project.

Initially our main unit of randomization was the PAs within the YNHH hospitalist service. The director of the hospitalist service, [name], and [name], Chief PA of the hospitalist service, both co-investigators on this proposal, have committed the participation of the PAs on the service to the protocol. The service includes 33 PAs who work during days Mon-Fri on non-critical care general medical units. There is a turnover rate of about 2 per year that nets 40 PAs during the 4-year data collection phase of the project. Prior to randomization, [name], [name] and other members of the study team will meet with the PAs during staff meetings, wherein we will describe the project and elicit interest. Thereafter, we will screen PAs for eligibility and obtain written consent for their participation. PAs will next complete baseline assessment, including an audio recorded sample of their usual manner of interviewing an inpatient with a substance use problem. Following baseline assessments, a restricted randomization procedure will be used to allocate an equal number of PAs to the three conditions (10 PAs per condition).

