General medical inpatient units have a patient population characterized by very high rates of co-morbid substance use disorders typically in excess of rates found in other primary care settings.¹ Moreover, large numbers of hospitals have adopted the hospitalist model for inpatient care on medical units,¹⁰⁹ and almost all hospitals have psychiatric CL services for addressing mental health and addiction problems that fall outside the expertise of medical providers.^{17,110} This study has the potential to identify highly disseminative strategies for integrating substance abuse services into primary care in a major sector of the U.S. health care system.

The practice under study for implementation is a single 20-min MI session that we have used to train medical students and physicians^{21,89} and are currently comparing to a computerized MI approach with substance using women in outpatient primary care treatment.⁸⁷ The MI session includes six steps: (1) understand patient's view of his/her substance use and motivations for change; (2) discuss reasons for using vs. not using/cutting down; (3) provide personalized feedback about patient's substance use; (4) continue handling resistance skillfully and draw out change talk; (5) develop a change plan or present change options for later consideration; and (6) summarize and support what the patient has decided to do. Clinicians ask key questions at the conclusion of steps 2-4 to ascertain the patient's commitment to change. If the patient endorses a goal of quitting or cutting back substance use, the clinician immediately proceeds to Step 5. Thus, clinicians adapt MI to their specific patient's readiness to change, giving the manualized treatment flexibility to avoid a rigid application of MI that might undermine its effectiveness and acceptability to clinicians.^{24,46}

Healthcare providers will each receive the MI implementation strategy offered within their assigned condition. Separate workshop trainings will occur for Healthcare providers within conditions. Additional workshops will be conducted as needed if new Healthcare providers are recruited into the study. In each condition, all Healthcare provider as well as the Psychiatrists from CL in ORDER ONE will audio record their MI interviews to confirm the interviews have occurred and to permit MI integrity rating.

1. Workshop (See One)

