6. **Subject classification:** Check off all classifications of subjects that will be specifically recruited for enrollment in the research project. Will subjects who may require additional safeguards or other considerations be enrolled in the study? If so, identify the population of subjects requiring special safeguards and provide a justification for their involvement.

- | | | |
|--|--|--|
|  Children |  Healthy |  Fetal material, placenta, or dead fetus |
|  Non-English Speaking |  Prisoners |  Economically disadvantaged persons |
|  Decisionally Impaired |  Employees |  Pregnant women and/or fetuses |
|  Yale Students |  Females of childbearing potential | |

NOTE: Is this research proposal designed to enroll children who are wards of the state as potential subjects? Yes No (If yes, see Instructions section VII #4 for further requirements)

7. **Inclusion/Exclusion Criteria:** What are the criteria used to determine subject inclusion or exclusion?

1. Inclusion criteria for Healthcare provider participants :
 - Assignment to one of the general medical inpatient units at YNHH during day-time shifts; intensive care units will be excluded given the morbidity of patients in this setting.
 - Volunteer to serve as study clinicians, attend a workshop about MI, and possibly receive live supervision.

- Agree to all procedures of this trial (randomization to training condition and of assigned patients, audio recording MI sessions, and completing assessments).
2. Exclusion criteria for Healthcare provider participants:
 - Have been formally supervised to use MI with patients on the units.
 - Intend to give notice to YNHH that they plan to leave the hospital or are scheduled for medical or family leave such that they will not be able to interview 40 patients during the study period.
1. Inclusion criteria for patients are:
 - Are 18 years of age or older.
 - Acknowledge use of a substance within past 28 days and meets screening criteria consistent with substance (illicit drugs, licit drugs that are used in a non-medically indicated fashion, alcohol, or nicotine) use disorder.
 - Are willing to consent to audio recording of interview with the Healthcare provider or CL psychiatrist.

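### Replacing providers who leave does not correct condition-related attrition, and the plan does not say how replacements are allocated or whether leavers' patients are analysed

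*Combined protocol and SAP*

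**What the plan says.** All references are to the combined protocol and SAP.

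- **Attrition rule** (Section V, item 12, I.2, bullet on managing differential attrition). The plan first gives its expectation: "We do not expect differential attrition across conditions in that the rate of Healthcare provider job turnover is very low". It adds that study activities overlap with providers' usual work. The one remedy offered is: "in the event of Healthcare provider discontinuation in the trial, we will recruit new Healthcare provider hires to maintain a balanced design".
- **Turnover and pool** (Section V, item 3). The hospitalist service has 33 PAs. "There is a turnover rate of about 2 per year that nets 40 PAs during the 4-year data collection phase of the project". Section VII, item 1 widens the pool beyond PAs: "Between the PAs and other healthcare providers we intend to enroll 30-40 participants".
- **Allocation** (Section V, item 3). After baseline assessment, a restricted randomisation allocates ten PAs to each of the three conditions. Replacements are not mentioned.
- **Late entrants** (Section V, item 3). Workshops are run separately by condition. "Additional workshops will be conducted as needed if new Healthcare providers are recruited into the study". How such providers are assigned is not described.
- **Eligibility** (Section V, item 7). Provider participants must accept randomisation to a training condition. Excluded are those who "Intend to give notice to YNHH that they plan to leave the hospital" or have leave scheduled that would stop them reaching 40 patients.
- **Outcome** (Section V, item 3). Uptake is a percentage of each provider's 40 consecutively enrolled patients, and providers are followed until they reach that number. No rule covers a provider who stops earlier, and no intention-to-treat rule for providers is stated.
- **Model** (Section V, item 12, I.2). Linear and generalised linear mixed models with random provider effects are planned.

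**The concern.** The rule is filed under differential attrition but acts only on head-counts. If leaving is related to the condition, the providers who remain in an arm are a selected group. Adding someone else to that arm restores the number, not the comparability that randomisation gave.

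Two gaps then matter. If a replacement goes to whichever arm has the vacancy, the assignment is known before that provider is recruited, so part of the comparison is no longer randomised. Replacements also enter later, are new to the hospital and may come from another profession. If, in addition, a leaver's patients drop out of the analysis because the caseload of 40 was never reached, the arm's result describes those who stayed plus those chosen to fill in.

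Condition-related leaving is conceivable on the plan's own account. The Background (Section V, item 2) warns that the apprenticeship approach may clash with clinicians' role and available time, and describes ordering from the consultation service as an easy, low-burden step. Discontinuation is also wider than leaving the job, because Section VII, item 9 makes continued participation voluntary.

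**Working it through.** **1. How far the design rests on ten providers per arm (Table 2).** For d = 0.4, two-sided alpha 0.05 and 80% power, n per arm = 2(1.960 + 0.842)² / 0.4² = 98.1, rounded up to 99. The t-based value is 100, giving 300 for three arms, as stated. The design effect is 1 + (31 − 1) × 0.07 = 3.1, and 300 × 3.1 = 930 = 30 × 31. For 40% vs 18%, the calculation gives 66 per arm, or 198, against the stated 195. The design effect is 1 + (17 − 1) × 0.10 = 2.6, and 195 × 2.6 = 507, against the stated 510 = 30 × 17. The totals before the uptake adjustment therefore reproduce, with about ten providers per arm.

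**2. How many leavers to expect.** The rate is 2/33 = 6.1% a year.
- Among 30 providers: 30 × 2/33 = 1.8 a year, and 1.8 × 4 ≈ 7.3 over four years.
- Compounded: 30 × (1 − (31/33)⁴) = 6.6.
- Per arm: 2 to 3.

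This is an upper bound on job turnover. It exposes every provider for all four years, although follow-up ends at 40 patients, and it ignores the exclusion of planned leavers. The documents give no figure for withdrawal from the study by providers who stay in post, or for turnover among non-PA providers.

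**3. Where a replacement goes if balance is the goal.** After one departure the arms stand at 10, 10 and 9. Placing the replacement in the vacated arm gives 10/10/10; either other placement gives 11/10/9. Only one of three placements restores balance, whereas simple 1:1:1 randomisation would choose it one time in three. A rule that must restore ten per condition therefore fixes the assignment in advance.

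**4. What equal head-counts do to bias.** Let a share *s* of an arm's providers leave, with means μ_S for stayers, μ_L for leavers and μ_R for replacements.
- Mean of the arm as randomised: (1 − *s*)μ_S + *s*μ_L.
- Mean after replacement, if leavers' data are not used: (1 − *s*)μ_S + *s*μ_R.
- Difference: *s*(μ_R − μ_L).

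Nothing about equal numbers makes this zero. If leavers' data are kept, the expression takes another form, which depends on how many patients they had reached.

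**5. Illustrative size, on assumptions not in the documents.** Suppose *s* = 0.1 to 0.3 in one arm only, leavers' data unused, and replacements differing from leavers by *g* = 0.5 to 2 provider-level SDs. The shift is *s* × *g* × √ICC in total SDs.
- ICC 0.07: from 0.1 × 0.5 × 0.265 = 0.01 to 0.3 × 2 × 0.265 = 0.16.
- Over the plan's ICC range of 0.05 to 0.10: 0.01 to 0.19.

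Against the planned d of 0.4, that runs from trivial to just under half.

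**6. Efficiency cost of unequal arms.** The variance of a pairwise contrast is proportional to 1/k₁ + 1/k₂. For 10 vs 10 it is 0.200. For 10 vs 9 it is 0.211, which is 5.6% more variance and a standard error 2.7% larger. For 10 vs 8 it is 0.225, with a standard error 6.1% larger.

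**The case against.** A reader might infer that the plan fills vacancies by arm instead of by randomisation. The documents do not say so; they are silent on how replacements are assigned. Equal allocation is also the aim of the restricted randomisation itself, agreement to be randomised is an entry criterion with no exception for late recruits, and the target of 30 to 40 providers leaves room for new entrants. These passages make it possible that replacements were meant to be randomised, but none says it. That part of the objection stands, and filling by arm can be put only as what the rule implies if taken literally.

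A reader might also put a definite number of percentage points of uptake on the bias. That would require leavers' data to be discarded entirely, an invented uptake for leavers, and all departures in one arm. No passage says leavers' patients are dropped, the mixed model can use providers with fewer sessions, and the plan's 80% uptake is an estimate across conditions, not for one arm. Such a figure would also measure the loss of leavers' data, which can bias the result even when replacements are randomised.

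Further points in the plan's favour: the extra burden in DO ONE is one supervised session plus an offered refresher; baseline equivalence and data availability are to be compared across conditions, with adjustment for imbalances; and replacement protects power. At d = 0.4, ICC 0.07 and 32 sessions per provider (80% of 40), power is 0.81 with ten per arm, 0.72 with eight and 0.66 with seven.

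The power argument supports recruiting more providers, not steering them to a particular arm. Covariate adjustment reaches measured differences only. Neither point makes equal numbers a remedy for condition-related leaving.

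**Conclusion.** The point holds in a limited form, as a cheap improvement. The plan's sole strategy for differential attrition does not address it, and two rules it needs are missing: how later recruits are allocated, and how a provider who stops short of 40 patients is analysed. Restoring ten per condition, taken literally, makes a replacement's arm predictable.

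This does not show that the comparison is biased. The size of any bias cannot be derived from the documents. The 0.01 to 0.19 SD range rests wholly on assumed differences between leavers and replacements, departures confined to one arm, and unused leaver data. About 7 leavers among 30 is a ceiling on job turnover, not a forecast.

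**What to change.** Replace the attrition rule with:

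> All randomised providers and all their enrolled patients are analysed in the assigned condition, whatever number of patients was reached. Any provider recruited later is allocated by the concealed randomisation schedule, not to the vacated arm. A sensitivity analysis is restricted to the originally randomised providers, and leavers are reported by arm.

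Recruitment of further providers continues, so the protection of power is kept. If replacements were always meant to be randomised, this only writes that down. The cost is wording plus arms that may end slightly unequal. The planned mixed models do not need equal numbers of providers, and the loss of efficiency is small: a 2.7% larger standard error at 10 vs 9. Patients already enrolled under leavers also remain in the analysis.
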